### **9.3 SAMPLE SIZE, POWER, ACCRUAL RATE AND STUDY DURATION**

#### **9.3.1 SAMPLE SIZE AND POWER**

The primary goal of this pilot study is to help identify unforeseen problems with a subsequent larger-scale clinical trial. We predict that there is a 20% probability that a particular patient's treatment plan will fail to meet all dosimetric constraints, most notably the 700 cc critical volume constraint for the liver minus GTV since many cirrhotic patients have small total liver volumes, rendering them ineligible for SBRT. A sample size of 15 patients will ensure that we will encounter at least one incidence of SBRT ineligibility at a 95% CI.

### **9.4 HANDLING OF MISSING DATA**

Every attempt will be made to obtain data at the defined time points as described in the primary and secondary endpoints. For time points that have no data, we will evaluate whether or not the other time points can be used to fulfill the primary and secondary data. If the data are not sufficient to analyze specific endpoints, the participant's data may be excluded entirely or partially, depending on the specific endpoints in question and in consultation with the biostatistician. No missing data will be imputed. Whenever possible, all available data will be included in the analysis. A sample size for each analysis will be clearly stated along with the reason for exclusion, if any participant is excluded from the analysis due to missing data.

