#### 3.2 STUDY ENDPOINTS

##### 3.2.1 PRIMARY ENDPOINT

Endpoint	Start	End
Proportion of participants who are transplanted or with localized disease control that meets Milan criteria (Section 7.5) within 1 year	Start of SBRT	Time of progression, or transplantation, or 1-years after last SBRT dose, whichever occurs first

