##### 3.2.2 SECONDARY ENDPOINTS

Endpoint	Start	End
1. Localized control rate: Incidence of progressive disease within or at the planned tumor volume (PTV) margin		Time of progression, transplantation, death or 2-years after last SBRT dose, whichever occurs first.
2. Incidence of intrahepatic progressive disease		
3. Incidence of extrahepatic progressive disease		
4. Proportion of participants that proceed to transplantation	First dose of SBRT	
5. Overall Survival		Time of death or 2-years after last SBRT dose
6. Incidence of non-classic RILD, defined as grade 4 aspartate aminotransferase or alanine aminotransferase elevation, or an increase in CP score of $\geq 2$ within 1 week to 3 months after completing SBRT (Appendix A)		3 months after last SBRT dose

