#### **6.5 FOLLOW-UP**

Participants will be followed and disease assessments will take place 6 weeks following completion of SBRT, then every 3 months up until enrollment on hospice or death, or 2 years from time of last SBRT dose, whichever occurs first. Follow-up visits will be consistent with standard of care, and assessments are listed in Section 6.8. Any participants removed from protocol therapy for unacceptable AE(s) will be followed until resolution or stabilization of the AE.

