#### 9.2.2 ANALYSIS OF PRIMARY ENDPOINT

Using the efficacy analysis set, the proportion of transplant eligible participants at 1 year (per Milan criteria, Section 7.5) will be measured from time of first SBRT dose, reported with 95% exact confidence interval (CI).

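### Section 9.4 lets participants without 1-year data be excluded from the primary proportion or judged at an unspecified visit, and no rule classifies death, hospice entry or withdrawal before 1 year

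*Combined protocol and SAP*

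**What the plan says.** - **Section 9.4 (missing data)** covers the primary and secondary endpoints. If a time point is empty, the team considers whether another can serve. If the data are still insufficient, the participant's "data may be excluded entirely or partially, depending on the specific endpoints in question", in consultation with the biostatistician. Imputation is ruled out. As safeguards, available data are to be used where possible, and each analysis reports its sample size and reasons for exclusion.
- **Section 3.2.1 (primary endpoint)** is "Proportion of participants who are transplanted or with localized disease control that meets Milan criteria (Section 7.5) within 1 year". Observation ends at "Time of progression, or transplantation, or 1-years after last SBRT dose, whichever occurs first". Death is not named.
- **Section 3.2.2 (secondary endpoints)** ends observation for several endpoints at "Time of progression, transplantation, death or 2-years after last SBRT dose, whichever occurs first". Death is named there.
- **Section 9.2.2 (primary analysis)** says that "the proportion of transplant eligible participants at 1 year (per Milan criteria, Section 7.5) will be measured from time of first SBRT dose", with an exact 95% interval. Transplantation is not mentioned.
- **Section 9.1** limits the efficacy analysis set to participants who received at least 85% of the prescribed dose.
- **Section 6.5** schedules assessments at 6 weeks, "then every 3 months up until enrollment on hospice or death", or to 2 years. Section 4.6 ends contact when consent is withdrawn. The Synopsis also ends follow-up at progression and at transplantation.

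No section says whether a participant who dies, enters hospice or withdraws before 1 year without a transplant counts as not eligible.

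**The concern.** The primary result is one proportion in about 15 people, so the handling of two or three participants can move it a long way. Participants have Child-Pugh B8 or worse cirrhosis. Those whose assessments stop at hospice, death or withdrawal are unlikely to be a random subset, and most would not be transplant eligible at 1 year. Excluding them shrinks the denominator without touching the numerator. Judging them on an earlier favourable scan adds them to the numerator. The exact interval reflects binomial sampling only and carries none of this.

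The opposite error is also possible. A transplanted participant is a success under Section 3.2.1 but may have no Milan assessment at 1 year. Read literally, Section 9.2.2 could leave that participant without data and open to exclusion.

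No hypothesis test is at stake. However, Section 1.3 says the pilot should estimate bridging efficacy against historical controls for a larger trial, so the estimate itself will be used.

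**Working it through.** **The plan's own figure.** The plan states no expected eligibility rate and no missingness rate. Its only relevant number is N = 15 (Section 9.3.1), from a 20% chance of dosimetric ineligibility and 95% confidence of seeing at least one case: ln(0.05)/ln(0.80) = 13.43, rounded up to 14. At 15 the chance is 1 − 0.80^15 = 96.5%. So N = 15 reproduces, but it says nothing about the precision or completeness of the primary proportion.

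**Inputs for the illustration (assumptions).** 15 in the efficacy set, x = 9 eligible or transplanted, m = 3 lost to death, hospice or withdrawal without transplant. Intervals are Clopper-Pearson 95%.

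| Handling of the 3 losses | Formula | Result |
|---|---|---|
| Counted as not eligible | x/15 | 9/15 = 60.0% (32.3 to 83.7) |
| Excluded | x/(15 − m) | 9/12 = 75.0% (42.8 to 94.5) |
| Judged eligible at an earlier visit | (x + m)/15 | 12/15 = 80.0% (51.9 to 95.7) |

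**Range.** Excluding m losses rather than counting them as not eligible adds x/(15 − m) − x/15 = xm/[15(15 − m)]. For x from 6 to 10:
- m = 1: +2.9 to +4.8 points
- m = 3: +10.0 to +16.7 points
- m = 5: +20.0 to +33.3 points

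**Opposite direction.** If instead 3 of the 9 successes are transplanted participants without a 1-year scan and they are excluded, the result is 6/12 = 50.0% (21.1 to 78.9) against 9/15 = 60.0%. If 3 not-eligible losses and t transplanted participants are all excluded, the result is (9 − t)/(12 − t): 66.7% at t = 3, 62.5% at t = 4 and 57.1% at t = 5. In this example the net error stays upward until five of the nine successes are also lost.

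**How common early death might be.** Section 1.2.1 cites a median survival of 17.0 months in a Child-Pugh B cohort. Assuming exponential survival, 1 − 0.5^(12/17) = 38.7% die by 12 months, or 15 × 0.387 = 5.8 participants. That cohort was not a transplant-listed B8-or-worse population, so this gives only an order of magnitude.

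**Is there a scan at 1 year?** Sections 6.5 and 6.8 place imaging at 6 weeks after SBRT, then every 3 months, ±4 weeks. Six weeks is 42/30.44 = 1.38 months, and four weeks is 0.92 months. Counted from the 6-week visit:
- 1.38 + 9 = 10.38 months, window 9.46 to 11.30
- 1.38 + 12 = 13.38 months, window 12.46 to 14.30

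One year after the last dose (12.0 months) falls between these windows. So does one year after the first dose, which is about 11.7 months after the last if treatment takes roughly 10 days (0.3 month). On this reading, some use of a neighbouring visit is unavoidable. If the 3-month steps run from the end of SBRT instead, a visit does fall at 12 months. The text does not settle which is meant.

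**The case against.** A reader might infer that Section 9.4 is certain to inflate the result. The documents do not support that. Exclusion is permitted, not required. It applies only when data are insufficient, after efforts to obtain them, and available data are to be used where possible.

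A reader might also infer that deaths will be treated as missing data. No section says so. Death is observed for overall survival, and the efficacy set depends only on dose received. It is therefore reasonable to read a participant known to have died as staying in the denominator and not eligible. That reading is sensible, but it is not written down. Section 3.2.1 omits death while Section 3.2.2 names it, and hospice entry and withdrawal lack even that much guidance.

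Nor do the documents show that exclusions will be decided after the outcomes are seen, because Section 9.4 gives no timing. And a missing scan need not mean a bad outcome, since follow-up also ends at transplantation.

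Two further points carry weight. Because a scheduled scan may not fall at 12 months, using an adjacent visit is not a fault in itself; the fault is that the choice is left open. And in a 15-person pilot with no test and no success threshold, wide overlapping intervals and mandatory reporting of exclusions limit the harm. Reporting makes an exclusion visible, but it does not correct the headline proportion.

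**Conclusion.** The concern holds as a risk of bias that the text permits. Section 9.4 allows exclusion or an unspecified substitute visit for the primary endpoint and bars imputation, and no other section fills the gap for death, hospice entry or withdrawal. Upward bias is the likely direction where those events cause the losses. Downward bias is possible if transplanted participants are excluded under the wording of Section 9.2.2.

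With 3 of 15 lost and none of them truly eligible, exclusion adds 10.0 to 16.7 points for 6 to 10 successes, and judging all three eligible at an earlier visit adds 3/15 = 20 points. These sizes rest on assumed counts. With no losses the problem does not arise.

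**What to change.** For the primary endpoint:

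1. Remove the discretionary exclusion and classify every participant in the efficacy analysis set. Transplanted by 1 year is a success. Death, hospice entry or withdrawal before 1 year without a transplant, or no qualifying scan, is not eligible. State that this endpoint definition takes precedence over the bar on imputation.
2. Pre-specify a 1-year scan window wide enough to contain a scheduled visit, name the visit that counts if two fall inside it, and say whether the 3-month steps run from the 6-week visit or from the end of SBRT. Too narrow a window would fail stable participants through the calendar alone.
3. Align Section 3.2.1 (within 1 year, transplanted or Milan, ending relative to the last dose) with Section 9.2.2 (at 1 year, Milan only, measured from the first dose).
4. Add a sensitivity analysis that counts missing cases other than deaths as eligible.

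The cost is a few sentences, one extra analysis line and a possibly less favourable proportion. No new data or visits are needed. Whether the denominator should be everyone who started SBRT rather than the 85%-dose set is a separate question, and this fix does not depend on it.

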## 10. CLINICAL MONITORING

## 10.1 OHSU KNIGHT CANCER INSTITUTE DATA & SAFETY MONITORING PLAN

This study is under the oversight of the Knight Cancer Institute's DSMC as described in the Knight institutional DSMP. The Knight DSMP outlines the elements required to ensure the safety of clinical trial participants, the accuracy and integrity of the data and the appropriate modification of cancer-related clinical trials for which significant benefits or risks have been discovered or when the clinical trial cannot be successfully concluded. The Knight DSMP also describes the methods and procedures for ensuring adequate oversight of cancer-related research at OHSU.

As described in the Knight DSMP, regardless of a trial's risk level and any specific Knight oversight in place, the Investigator is singularly responsible for overseeing every aspect of the design, conduct, and final analysis of his/her investigation.

The Knight DSMC will review and monitor study progress, toxicity, safety and other data from this study. Information that raises any questions about participant safety or protocol performance will be addressed by the Investigator, statistician and study team. Should any major concerns arise, the Knight DSMC may recommend corrective action and determine whether or not to suspend the study.

The Knight DSMC will review each protocol every 6 months, but may occur more often, if required, to review toxicity and accrual data (please refer to Knight DSMP for additional details on audit frequency). The Knight DSMC will review accrual, toxicity, response and reporting information. Information to be provided to the DSMC may include: participant accrual; treatment regimen information; AEs and SAEs reported by category; summary of any deaths on study; audit results; and a summary provided by the study team. Other information (e.g. scans, laboratory values) will be provided upon request.

## 10.2 CLINICAL DATA & SAFETY MONITORING

The OHSU Investigator is ultimately, singularly responsible for overseeing every aspect of the investigation, including design, governing conduct at all participating sites, and final analysis of study data.

In the absence of a formal monitoring plan, the Investigator may work with his/her study team to conduct and document internal monitoring of the study to verify protection of human participants, quality of data, and/or ongoing compliance with the protocol and applicable regulatory requirements.

If at any time Investigator noncompliance is discovered at OHSU, the Investigator shall promptly either secure compliance.

Independent audits will be conducted by the Knight DSMC to verify that the rights and well-being of human participants are protected, that the reported trial data are accurate, that the conduct of the trial is in compliance with the protocol and applicable regulatory requirements, and that evidence of ongoing investigator oversight is present.

## 10.3 QUALITY ASSURANCE & QUALITY CONTROL

The investigational site will provide direct access to all trial related source data/documents, and reports for the purpose of monitoring by the monitor and/or sponsor, and auditing by the Knight DSMC and/or regulatory authorities.

Quality assurance (QA) auditing activities will occur as detailed in the Knight DSMP. All discrepancies, queries, deviations, observations, and findings will be compiled into a final audit report along with a Corrective and Preventative Action Plan.

The Sponsor-investigator, or study monitor, will verify that the clinical trial is conducted and data are generated, documented (recorded), and reported in compliance with the protocol, GCP, and the applicable regulatory requirements (e.g., Good Laboratory Practices (GLP), Good Manufacturing Practices (GMP)).

## **11. DATA HANDLING AND MANAGEMENT RESPONSIBILITIES**

### **11.1 SOURCE DATA/DOCUMENTS**

The Investigator is responsible for ensuring the accuracy, completeness, legibility, and timeliness of the data reported. All source documents should be completed in a neat, legible manner to ensure accurate interpretation of data. The Investigator will maintain adequate case histories of study participants, including accurate CRFs, and source documentation.

### **11.2 PARTICIPANT & DATA CONFIDENTIALITY**

The information obtained during the conduct of this clinical study is confidential, and unless otherwise noted, disclosure to third parties is prohibited. Information contained within this study will be maintained in accordance with applicable laws protecting participant privacy, including the provisions of the Health Insurance Portability and Accountability Act (HIPAA).

Participant confidentiality is strictly held in trust by the participating Investigator(s) and study team. This confidentiality is extended to cover testing of biological samples and genetic tests in addition to the clinical information relating to participants. Therefore, the study protocol, documentation, data, and all other information generated will be held in strict confidence. No information concerning the study or the data will be released to any unauthorized third party without prior written approval of the sponsor.

The study monitor, other authorized representatives of the sponsor, representatives of the IRB or manufacturer supplying study product may inspect all documents and records required to be maintained by the Investigator, including but not limited to, medical records (office, clinic, or hospital) and pharmacy records for the participants in this study. The clinical study site will permit access to such records.

Upon enrollment, participants will be assigned a code that will be used instead of their name, medical record number or other personally identifying information. Electronic files for data analysis will contain only the participant code. Codes will not contain any part of the 18 HIPAA identifiers (e.g., initials, DOB, MRN). The key associating the codes and the participants' personally identifying information will be restricted to the Investigator and study staff. The key will be kept secure on a restricted OHSU network drive in a limited access folder.

The study participant's contact information will be securely stored at each clinical site for internal use during the study. At the end of the study, all records will continue to be kept in a secure location for as long a period as dictated by local IRB and institutional regulations. Study participant research data, which is for purposes of statistical analysis and scientific reporting, will be transmitted to and stored within the Knight Cancer Institute per [OHSU's Information Security Directives](#). Individual participants and their research data will be identified by a unique study identification number. The study data entry and study management systems used by clinical sites and by Knight Cancer Institute research staff will be secured and password protected per [OHSU's Information Security Directives](#). At the end of the study, all study databases will be de-identified and archived within the Knight Cancer Institute.

### **11.3 DATA COLLECTION & STORAGE: PRIVACY, CONFIDENTIALITY & SECURITY**

Data collection is the responsibility of the clinical trial staff at the site under the supervision of the site Investigator. The Investigator is responsible for ensuring the accuracy, completeness, legibility, and timeliness of the data reported. Standard institutional practices will be followed as described in the [OHSU's Information Security Directives](#) to maintain the confidentiality and security of data collected in this study. Study staff will be trained with regard to these procedures.

Loss of participant confidentiality is a risk of participation. Efforts will be made to keep study participant identities confidential except as required by law. Participants' samples will be identified by code only. Specifically, each consenting participant will be assigned a unique coded identifier consisting of numbers. This identifier will be associated with the participant throughout the duration of their participation in the trial. The coded identifier will also be used to identify any participant specific samples.

Basic accrual tracking information (demographic, consent, visit information) will be captured in OHSU's electronic clinical information research system (eCRIS), hosted on OHSU secure servers and managed by OHSU's information technology group at their data center in downtown Portland, Oregon. Any additional printed documents containing participant identifiers, such as those from the medical record to confirm eligibility, will be filed in binders and kept in a locked, secure location.

Study outcome data will be captured in electronic case report forms (eCRFs) using an electronic data capture (EDC), REDCap, system on OHSU secure servers, which facilitates information being stored in a unified format and location. To further preserve confidentiality, PHI in the EDC system will be limited to just birth date and visit dates. The web-accessible EDC system is password protected and encrypted with role-based security, and administered by designated informatics staff within OHSU or Knight Cancer Institute. All users of the database are assigned a unique ID, username, and password and must complete training appropriate to their role before they are authorized to enter, access, and store data in the database.

Data from correlative studies will be entered into the EDC system by study personnel at OHSU. All other electronic data extracts will be stored only on OHSU computers and restricted drives, limited only to study investigators and staff with authorization to access the data. Quality assurance will be conducted as outlined in Section 10.3, Quality Assurance & Quality Control.

#### **11.4 MAINTENANCE OF RECORDS**

Records and documents pertaining to the conduct of this study, source documents, consent forms, laboratory test results and medication inventory records, must be retained by the Investigator for a period of 2 years following the date a marketing application is approved for the drug for the indication for which it is being investigated; or, if no application is to be filed or if the application is not approved for such indicate, until 2 years after the investigation is discontinued and FDA is notified. It is the responsibility of the sponsor to inform the Investigator when these documents no longer need to be retained.

If the Investigator relocates or for any reason withdraws from the study, the study records must be transferred to an agreed upon designee, such as another institution or another investigator at OHSU. Records must be maintained according to institutional or FDA requirements.

## 11.5 PUBLICATION AND DATA SHARING POLICY

This study will comply with the NIH Public Access Policy, which ensures that the public has access to the published results of NIH funded research. It requires scientists to submit final peer-reviewed journal manuscripts that arise from NIH funds to the digital archive PubMed Central upon acceptance for publication.

This study will adhere to the requirements set forth by the ICMJE and FDAAA that requires all clinical trials to be registered in a public trials registry (e.g., ClinicalTrials.gov) prior to participant enrollment.

## **12. ETHICS/PROTECTION OF HUMAN PARTICIPANTS**

### **12.1 ETHICAL STANDARD**

The Investigator will ensure that this study is conducted in full conformity with Regulations for the Protection of Human Participants of Research codified in 45 CFR Part 46, 21 CFR Part 50, 21 CFR Part 56, and/or the ICH E6.

